**LIST OF ACRONYM AND DEFINITIONS**

|              |   |
|--------------|---|
| AE    | Adverse event  |
| CI    | Clinical Investigation   |
| CIP   | Clinical Investigation Plan  |
| CV    | Curriculum Vitae   |
| CRF   | Case Report Form   |
| EC    | Ethics Committee   |
| EDC   | Electronic Data Capture System   |
| EQ-5D | A standardized health-related quality of life instrument by the EuroQuol Group |
| FAAM  | Foot and Ankle Ability Measure   |
| GCP   | Good Clinical Practices  |
| GMP   | Good Manufacturing Practice  |
| ICH   | International Conference on Harmonization                                      |
| ID    | Investigational Device   |
| IRB   | Institutional Review Board   |
| PI    | Principle Investigator   |
| PROM  | Patient Reported Outcome Measure   |
| REC   | Research Ethical Committee   |
| SAE   | Serious Adverse Event  |
| USAEE | Unexpected Serious Adverse Event   |

## 1.0 Synopsis

|  |  |
|--|--|
| Sponsor                                   | Wright Medical  |
| Clinical Investigation Title              | Wright Foot & Ankle Post-Market Observational Study   |
| Device Name and Description               | Data will be collected only for approved or cleared Wright Medical products   |
| Intended Use and Indications for Use      | The Instructions for Use (IFU) for each individual product can be found at http://www.wright.com/prescribing-use-3 or can be provided at your request   |
| Clinical Investigation Purpose / Rational | Collect data needed to satisfy the Medical Device Regulations (MDR)   |
| Clinical Investigation Design             | Global, multi-center, post-market observational study. Data will be collected at baseline, surgery, at last scheduled standard of care and/or surgeon release follow-up (FU) time point. Additionally, PROMs and safety may be followed yearly to sufficiently assess the safety of the product over the clinical lifetime as needed based on the current risk analysis for the product.  |
| Clinical Investigation Objectives         | Demonstrate the safety and performance of the Wright product by: 
 
Comparing the improvements in patient-reported pain and social interaction for quality of life from pre-op through post-operatively, assessed by the EQ-5D-5L.
 
Comparing the improvement in patient-reported function scores from pre-op through post-operatively, assessed by the FAAM
 
Identifying and reporting the safety of the implant in terms of complications and adverse events.
 
Conducting a surgeon survey including radiographic assessment of fusion and consolidation time
 
Conducting patient surveys to assess current implant status (to include complications)
 
 |
| Clinical Investigation Endpoints          | Patient Outcome Measures (EQ-5D and FAAM) and adverse events  |
| Inclusion Criteria                        | Subjects to be included in the study must meet all of the following criteria:   |

|   |   |
|---|---|
|   | 
 
• Willing and able to consent to participate (written, informed consent);
 
• Willing and able to attend/complete the requested follow-up visits;
 
• Considered for treatment with one or more approved or cleared Wright Medical products included in this study
 
  |
| Exclusion Criteria                                   | Subjects will be excluded from the study if they meet any of the following criteria: 
 
• Subjects determined, by the investigator, to be an inappropriate candidate for the procedure indicated;
 
• Unable to consent to participate (written, informed consent);
 
• Unable to attend/complete the requested follow-up visits
 
 |
| Visit Schedule                                       | Pre-op/Op, and Last scheduled standard of care and/or surgeon release follow-up (FU) time point. Additionally, PROMS and safety may be followed yearly to sufficiently assess the safety of the product throughout the defined product clinical lifetime as needed based on the current risk analysis for the product.  |
| Statistical Methods                                  | Descriptive statistics, Kaplan Meier survival analysis and Life tables  |
| Duration of Clinical Investigation                   | Expected enrollment is 5 years
Based on varied definitions of product clinical lifetime, the follow-up period will be 12wks to 10 years  |
| Number of Sites and Subjects                         | $n =$ a minimum of 40 patients per device or until sufficient data is collected to satisfy the notified bodies
5 to 15 sites   |
| Committees (e.g., safety, steering) and/or Core Labs | none  |

## 2.0 **Background**

The European Union (EU) Medical Device Regulation (MDR) 2017/83/EC is a new regulation that applies to all medical device manufacturers who intend to market their products in the EU. The EU MDR has increased the requirements for clinical data needed for products to maintain certification. Under the regulation, the manufacturer must proactively collect and evaluate clinical data to establish and verify:

- that under normal conditions of use, a device achieves the performance intended as specified by the manufacturer;
- the clinical benefits of a device as specified by the manufacturer;
- the clinical safety of the device;
  - Identify previously unknown side-effects;
  - Monitor the intended side-effects and contraindications;
  - Identify and analyze emerging risks on the basis of factual evidence;
- ensure the continued acceptability of the benefit / risk ratio; and
- systemic misuse or off-label use with a view to verify the intended purpose is correct.

Wright Medical is conducting this observational study to meet the new clinical data requirements for the EU MDR.

The purpose of this post-market clinical observational study is to demonstrate the safety and performance of the Wright product after implantation over standard follow-up period using patient reported outcome measures related to quality of life, pain and functional improvements, safety of the implants, as well as radiographic assessments (X-Rays).

The outcome measures collected in this study will be analyzed and reported as required for local, regional, and country requirements (i.e., regulatory authorities and notified bodies).

### **3.0 Identification and Description of Device**

#### **3.1 Summary description**

Data will be collected only for approved or cleared Wright Medical products

#### **3.2 Manufacturer Details**

Wright Medical is the manufacturer or distributor for all devices. These products are manufactured according to International Conference on Harmonization (ICH) Good Clinical Practices (GCP) in accordance with applicable Good Manufacturing Practice (GMP) and ISO 14155:2011: through relevant manufacturing and related validation processes.

#### **3.3 Device and Components**

All products in the table below can be included in the study. Additional products may be added as they become available for this post-market study

| Wright Products |   |
|------------------------------------|---|
| VALOR                       | HV Screws                                  |
| ALLOMATRIX                  | Jones Fracture                             |
| OSTEOSET                    | ORTHOLOC Forefoot Fracture                 |
| SWANSON TOES                | FUSEFORCE Staples                          |
| PRO-TOE VO                  | G-FORCE                                    |
| PRODENSE                    | ORTHOLOC 3Di Ankle Fracture Plating System |
| SYNCHFIX                    | SALVATION Plating                          |
| MIS BUNION                  | Quick Staple                               |
| BIOARCH                     | ORTHOLOC Calc Fracture                     |
| PHALINX                     | ORTHOLOC 3Di Small Bones                   |
| GRAVITY SUTURE ANCHORS      | ORTHOLOC 3Di Midfoot/Flatfoot              |
| ORTHOLOC 3Di                | CROSSCHECK 3Di                             |
| DARTFIRE                    | Biofoam Wedges                             |
| MICA Screws                 | Omnitech                                   |
| CHARLOTTE MUC Screws        | Omniveo                                    |
| SALVATION External Fixation | CHARLOTTE SNAP OFF SCREWS                  |
| SALVATION Beams & Bolts | TELYA                                      |

|                               |   |
|-------------------------------|---|
| DARCO Headless Screws  | UNIMA                                    |
| CLAW II Plating System | DARCO Plantar Lapidus                    |
| DARCO Headed Screws    | ORTHOLOC 3Di Ankle Fusion Plating System |

1 Not all products are available in all geographies

#### **3.4 Population and Indications for Use**

The Instructions for Use (IFU) for each individual product can be found at <http://www.wright.com/prescribing-use-3> or can be provided at your request.

#### **3.5 Traceability**

N/A

#### **3.6 Training required**

Clinical Research Sites will be identified to participate in the study based on current experience, and training in the use of the Wright Medical Products and according to ICH GCP guidelines and ISO 14155: 2011 which states; qualified by education, training and experience to perform his or her respective task(s). It is the expectation the surgeon will adhere to and follow each Wright Medical Product Surgical Technique and have knowledge of the contraindications as provided in the IFU.

#### **3.7 Surgical procedure**

Surgical Technique for each individual product can be found at <http://www.wright.com/healthcare-professionals/literature-videos> or can be provided at your request.

### **4.0 Risk/Benefit of the investigational device and clinical investigation**

#### **4.1 Potential Benefits**

This is an observational study, so participation may not result in direct benefit to the subject. The use of information contained within the database may be of future benefit to subjects undergoing certain orthopedic procedures.

#### **4.2 Potential Risks**

As this is observational study, there are no foreseeable risks of physical harm associated with participation in this study, since the study involves only data collection.

#### **4.3 Risk Minimization**

As this is an observational study, there no foreseeable risks to minimize.

### **5.0 Objectives and endpoints**

#### **5.1 Objective**

The objective is to demonstrate the safety and performance of the Wright product after implantation over standard follow-up period using patient reported outcome measures related to quality of life, pain and functional improvements, safety of the implants, as well as radiographic assessments (X-Rays)

**5.2 Hypotheses**

Show that Wright Products are safe and effective

**5.3 Intended Use**

IFU for each individual product can be found at <http://www.wright.com/prescribing-use-3> or can be provided at your request.

**5.4 Endpoints**

The primary endpoint is to demonstrate the safety and performance of the Wright product by:

- Comparing the improvements in patient-reported pain and social interaction for quality of life from pre-op through post-operatively, assessed by the EQ-5D-5L

Secondary endpoints:

- Comparing the improvement in patient-reported function scores from pre-op through post-operatively, assessed by the Foot and Ankle Ability Measure (FAAM)
- Identifying and reporting the safety of the implant in terms of complications and adverse events.
- Conducting a surgeon survey including radiographic assessment of fusion and consolidation time
- Conducting patient surveys to assess current implant status (to include complications)

**6.0 Design of the clinical investigation**

**6.1 Generalities**

**6.1.1 Clinical Investigation Design Summary**

The selected design is a global, multi-center, non-randomized, prospective observational study. The study subjects included are those treated with one or more approved or cleared Wright Medical products included in this study. Wright Medical may adjust enrollment requirements or close enrollment for a certain device due to the Sponsor's needs. Sites will be notified prior to any changes.

### 6.1.2 Methods and Timing for Assessing, recording and Analyzing Variables

| Procedures                                      | Pre-op/ Op | Final Clinical Follow-Up Visit
(Op to 1yr) | 1-10 yr
(-/+1 yr)
(yearly as necessary) | Study Close |
|--|-------------------|---|--|--------------------|
| Informed Consent                                | X                 |   |  |                    |
| Inclusion/Exclusion Criteria                    | X                 |   |  |                    |
| Medical History/Demographics                    | X                 |   |  |                    |
| Operative (Surgical) procedure/device           | X                 |   |  |                    |
| EQ-5D   | X                 | X   | X  |                    |
| FAAM  | X                 | X   | X  |                    |
| Surgeon Survey with radiographic assessment     |                   | X   |  |                    |
| Adverse Event Assessment                        | X                 | X   | X    |                    |
| Patient Survey                                  |                   |   | X  |                    |
| End of Study                                    |                   |   |  | X                  |
| Surgical Intervention               |                   |   |  |                    |
| *Sponsor-approved Unscheduled Visit |                   |   |  |                    |

1&2 These are not scheduled time point events but will be observed throughout study participation

 Only required when patient survey indicates an adverse event occurred

 Follow-up time points only executed if needed per device clinical lifetime definition

## 6.2 Subjects

### 6.2.1 Eligibility Criteria (Inclusion/Exclusion)

#### 6.2.1.1 Inclusion Criteria

Subjects to be included in the study must meet all of the following criteria:

- Willing and able to consent to participate (written, informed consent);
- Willing and able to attend/complete the requested follow-up visits;
- Considered for treatment with one or more approved or cleared Wright Medical products included in this study.

**6.2.1.2 Exclusion Criteria**

Subjects will be excluded from the study if they meet any of the following criteria:

- Subjects determined, by the investigator, to be an inappropriate candidate for the procedure indicated;
- Unable to consent to participate (written, informed consent);
- Unable to attend/complete the requested follow-up visits;

**6.2.2 Criteria and Procedures for Subject Withdrawal or Discontinuation**

Subjects maintain the right to discontinue their participation in the study at any point without penalty or loss of benefit to which the subject is otherwise entitled per ICH E6 4.8.10(m) guidelines. If at any time the study device is removed, the subject will be discontinued from the study unless the subject has other study devices remaining.

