**6.2.5 Expected duration of each subject's participation**

Based on varied definitions of product clinical lifetime, the follow-up period will be 12 weeks to 10 years

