**6.3.4 Schedule of Visits and Assessment Requirements**

Subjects will be seen pre-operatively, at the operative visit and prospectively at the Final Clinical Follow-Up visit required as determined by the physician as the last standard of care visit for the procedure performed.

Additionally, PROMS and safety may be followed yearly to sufficiently assess the safety of the product over the clinical lifetime as needed based on the current risk analysis for the product.

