Whenever the available data allows, the standard deviation, interquartile range (IQR) and maximum and minimum will be calculated. All quantitative variables will be assessed for normality via the Shapiro-Wilk test. The 95% confidence interval (CI) of the mean will be presented when the normality of the data is met.

All qualitative variables, including those based on summaries (secondary elements), will be analyzed listing the proportions, frequencies, column and row totals and missing proportion (if any).

The proportion of device surviving at each visit will be summarized for each device. Rates will be computed based on available data. Missing data will not be imputed.

No imputations for missing data will be conducted.

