## 8. Appendices

### 8.1. Appendix 1. List of Wright medical devices included in the study.

Device	Follow-Up Time Period
611 Nail	1 year
BIOARCH	1 year, 2 year
BIOFOAM Ankle Spacers	1 year
BIOFOAM Wedge System	1 year
CHARLOTTE MUC Screws	1 year
CHARLOTTE Quick Staple	1 year
CHARLOTTE Snap-Off Screws	1 year
CLAW II	1 year
DARCO Headed Screws	1 year
DARCO Headless Screws	1 year
DARCO MFS	1 year
DARCO MRS	1 year
DARCO Plantar Lapidus Plate	1 year
DART-FIRE	1 year
FUSEFORCE	1 year
FUTURA CSI	1 year, 2 year
G-FORCE	1 year, 2 year
GRAVITY SYNCHFIX	1 year, 2 year
HV Screws	1 year
MaxLock Edgelock Plate	1 year
MiniMaxLock ISO Plate	1 year
MICA Screws	1 year
NEXFIX Snap-Off Screws	1 year
Omni Evolution Screws	1 year
ORTHOLOC 2 Ankle Fracture	1 year
ORTHOLOC 2 CROSSCHECK	1 year
ORTHOLOC 2 Small Bones	1 year
ORTHOLOC 3Di Ankle Fusion	1 year
ORTHOLOC 3Di Hallux	1 year
ORTHOLOC 3Di Midfoot/Flatfoot	1 year
ORTHOLOC Forefoot Fracture	1 year
ORTHOLOC Plantar Lapidus	1 year
ORTHOLOC Calc Fracture	1 year
PHALINX	1 year
PITON	1 year
PRO-TOE VO	1 year
SALVATION ExFix	1 year
SALVATION Bolts and Beams	1 year
SALVATION 3Di Plates	1 year
SWANSON Toes	1 year, 2 year, 3 year, 4 year, 5 year, 6 year, 7 year, 8 year, 9 year, 10 year
Telya	1 year
UNIMA EVO and NEUTRA Screws	1 year
VALOR Nail	1 year

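### Protocol 6.2.2 ends participation at any device removal, so subjects whose only study device is the external fixator may exit before the 1-year follow-up in SAP Appendix 1

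*Protocol*

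**What the plan says.** - **Exit rule.** Protocol 6.2.2: "If at any time the study device is removed, the subject will be discontinued from the study". The only exception is a subject who still has another study device. The reason for removal plays no part.
- **Device.** Protocol 3.3 lists "SALVATION External Fixation" as a study product. SAP Appendix 1 lists "SALVATION ExFix" with a follow-up period of 1 year. Neither document exempts it from 6.2.2.
- **Timing of scores.** The first post-operative EQ-5D and FAAM, and the only surgeon survey, are taken at the "Final Clinical Follow-Up visit required as determined by the physician as the last standard of care visit for the procedure performed" (Protocol 6.3.4). The schedule in Protocol 6.1.2 lets this visit fall anywhere between the operation and 1 year. Yearly contacts are conditional: "Follow-up time points only executed if needed per device clinical lifetime definition". Across devices, "the follow-up period will be 12 weeks to 10 years" (Protocol 6.2.5).
- **Survivorship.** Under Protocol 7.3 the events are a device-caused adverse event and a reoperation to exchange or remove the device because the implant failed. Everyone else is censored at the last follow-up visit. SAP 3.1 adds: "The proportion of device surviving at each visit will be summarized for each device".
- **Disposition and missing data.** The reasons for discontinuation in SAP Table 1.1 are loss to follow-up, withdrawn consent, adverse event and a residual category. SAP 3.1 rules out imputation.

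**The concern.** For an implant meant to stay in place, removal usually signals a problem, and ending participation then affects few subjects. An external fixator is different if, as assumed here, taking it off is the normal end of its use. The exit rule then applies to the intended course of every subject who has no other study device. Such a subject must leave under Protocol 6.2.2 and must be followed to 1 year under SAP Appendix 1, and both cannot be met.

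At stake are the later EQ-5D and FAAM scores, the patient survey, and adverse events that arise after the frame is off. The disposition table is affected too: a completed course of treatment would be counted as a non-completion under *Other* or *Adverse event*.

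**Working it through.** **1. The plan's own figure.** No figure is in dispute. The sample size in Protocol 7.2 is reproduced because it is used in step 6. With SD 0.313, half-width 0.1 and two-sided alpha 0.05, n = (1.96 × 0.313 / 0.1)² = 37.63, rounded up to 38. This agrees with the protocol, which then plans 40 per device.

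**2. Who is caught by the rule.** It covers a subject whose fixator is removed and who has no other study device. SAP 3.1 notes that a patient may have received more than one device. Those subjects stay in.

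**3. What is lost, by timing of the Final Clinical Follow-Up visit** (fixator as the only study device):

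| Visit relative to removal | Post-operative EQ-5D, FAAM and surgeon survey | Data due after removal |
|---|---|---|
| At or before | Collected, so a change from baseline exists | Lost |
| After | Not collected, so no primary outcome | Lost |

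The second row is plausible. The visit is defined as the last one in standard care for the procedure. If taking off the frame is part of that care, the last visit falls at or after removal.

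**4. Survivorship.** Planned removal is not an event under Protocol 7.3. The subject is censored, and the Kaplan-Meier estimate remains available. The gap lies in the visit-by-visit proportion in SAP 3.1: neither document says whether a device removed without failure counts as surviving, as not surviving, or as outside the denominator.

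**5. Follow-up time lost.** The documents give no removal date. Assume week 8 to week 26 of a 52-week follow-up:

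- removal at week 8: (52 − 8)/52 = 44/52 = 85% lost
- removal at week 26: (52 − 26)/52 = 26/52 = 50% lost

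**6. Effect on precision (illustration only).** Suppose the planned 40 fixator subjects had been enrolled, and every one with no other study device lost the 1-year score. The half-width is 1.96 × 0.313 / √n.

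| Share with fixator as only study device | n with 1-year score | 95% half-width |
|---|---|---|
| 0% | 40 | 0.097 |
| 25% | 30 | 0.112 |
| 50% | 20 | 0.137 |
| 75% | 10 | 0.194 |
| 100% | 0 | not estimable |

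The share is not in the documents. The SD is that of a post-operative score, not of a change, so the table shows direction and rough size only.

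**7. Likely numbers.** SAP 3.1 reports 122 patients enrolled, and Appendix 1 lists 43 devices. That averages 122/43 = 2.8 patients per device if each received one device, and more if some received several. SAP 3.1 summarises only devices with at least 10 patients, so the fixator may appear in listings alone.

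**The case against.** A reader might infer that this device's endpoints cannot be scored at all, or that survival has no meaning for it. The documents do not support either reading. EQ-5D, FAAM and the surgeon survey are due at a visit set by the physician between operation and 1 year, and the primary analysis in SAP 3.1.1 names no time point. A subject seen at or before removal is therefore scored. Subjects with another study device are followed on. Adverse events up to exit are counted. Survivorship rests on failure, with censoring otherwise.

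It can also be argued that 1 year in Appendix 1 is only the outer limit of the clinical visit window, so that no separate 1-year contact is due. This is possible. However, the same column lists every year from 1 to 10 for SWANSON Toes, which looks more like a list of yearly contacts. Even on the narrower reading, a clinical visit after removal is still lost.

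Three further objections stand as limits on the point:

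- That the frame is temporary and comes off before 1 year is general device knowledge. It is not in the documents.
- The number of subjects with the fixator as their only study device is unknown and could be zero.
- Enrollment stopped on 1 November 2021, before the SAP took effect on 12 January 2022. A protocol change cannot recover data from subjects who have already exited.

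**Conclusion.** The conflict is real but narrow. Protocol 6.2.2 treats planned removal and removal for failure alike, whereas Protocol 7.3 separates them. For subjects whose only study device is the external fixator, this clashes with the 1-year period in SAP Appendix 1. Data due after removal are missing by rule. They include the only post-operative score when the Final Clinical Follow-Up visit comes after removal.

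The per-subject loss of 50% to 85% of a 52-week follow-up depends on the assumed removal at week 8 to 26, and on reading Appendix 1 as follow-up that runs to 1 year. The overall effect cannot be sized, because the number of affected subjects is not given. It is probably small: this is 1 of 43 devices, and it may fall below the 10-patient threshold. If so, it still matters for the study-completion listing, where planned removal would read as an early exit.

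**What to change.** **Protocol.** Reconcile 6.2.2 with 7.3 and with SAP Appendix 1, so that planned (non-failure) removal does not end study participation. The subject would still complete the Final Clinical Follow-Up visit and any yearly forms scheduled for the device.

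**SAP.**
- Give planned removal its own status in Table 1.1, separate from *Other* and *Adverse event*.
- Censor device time at the planned removal date. This is needed alongside the protocol change: if subjects stay in after removal, censoring at the last follow-up visit would credit the device with time when it was no longer in place.
- State how a device removed as planned enters the proportion surviving at each visit, for example by leaving the denominator from the removal date.
- State the limitation for subjects who have already exited under the present rule.

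**Cost.** One protocol sentence, with the ethics approval that Protocol 8.3 requires for an amendment, and a short SAP rule. On the reading of Appendix 1 taken here, no new contacts are needed. The protocol sentence helps only subjects still in follow-up, while the SAP rule is useful either way. The change concerns study participation and analysis only, and takes no position on when a frame should be removed.

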### 3. Statistical Procedure

#### 3.1. FRAMEWORK

The purpose of this statistical analysis plan is to guide the analysis and production of statistical output for the Wright Foot & Ankle Post-Market Observational Study. The company decided to discontinue enrollment to the study on November 1, 2021. At study end date, there were 122 patients enrolled in the study. The sample size of 40 patients per device that was originally planned in the study was therefore not met.

The study required at least 40 sample size for each Wright medical device (See INT19-MDR-001 Protocol, Version 3). For the same sample size parameters in the protocol  $n=10$ , will yield a power of 0.5. Thus, for the purpose of reporting statistically valid outcomes, descriptive summary statistics will be presented for Wright devices implanted in at least 10 patients enrolled in the study. Patient data on devices that has less than 10 implanted patients will be provided in the listings to be made available for future study or reference. Appendix Table 1 lists the Wright devices that are included in the study.

As the goal of the study is to determine the performance and safety of each device under investigation, analysis of outcomes will be done for each device the patient received. Note that a patient may have received more than one of the Wright devices. In all analysis of outcomes, patient level data will be included in the analysis for each device he/she received.

All analysis to be conducted are of descriptive nature only. No test of hypothesis will be performed. All quantitative variables, including those based on calculations (i.e., improvement from baseline), will be analyzed with a case summary evaluation before the detailed characteristics and parameter can be evaluated. A case summary contains a listing of the number of valid cases/values, missing cases/values (if any) and total cases/values in the specific analysis. The mean and median will be reported to assess the average or centrality of quantitative variables. Improvement from baseline in patient reported outcome (PROM) will be assessed at each post-surgery visit. Improvement will be based on the difference in raw scores.

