### 3.1.1. Primary Analysis / Endpoint

Improvements in subject quality of life after surgery will be assessed by constructing 95% confidence interval for the mean change from baseline score in EQ-5D-5L.

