#### 4.6. MISSING DATA

The intent is to collect as complete a dataset as possible. Nevertheless, in some situations missing data cannot be avoided. The reports and tables therefore will show the number and percentage of missing cases for each analyzed variable in relation to the enrolled cases for each post-operative assessment.

Missing data will be reported for each variable or calculation (if any) and overall totals will be reported including the proportion of missing data (if any).

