### 5. Population and Progress

All analysis will include all subjects implanted with any of the Wright devices listed in Appendix 1, hence called Treated population.

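### Subjects whose only study device is removed leave the study and nothing is imputed, so per-device EQ-5D and FAAM change describes subjects still followed and probably overstates improvement where removal follows failure or a complication

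*Protocol*

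**What the plan says.** - Protocol 6.2.2: on removal of the study device at any time, "the subject will be discontinued from the study unless the subject has other study devices remaining". The trigger is removal for any reason.
- SAP 3.1.1, the primary analysis, rests on "constructing 95% confidence interval for the mean change from baseline score in EQ-5D-5L". SAP 3.1 applies this device by device and at each visit after surgery. SAP 3.1.2 treats FAAM change in the same way.
- SAP 3.1: "No imputations for missing data will be conducted". SAP 4.6 adds only that reports will "show the number and percentage of missing cases for each analyzed variable". No sensitivity analysis for removal is planned.
- SAP 5: "All analysis will include all subjects implanted with any of the Wright devices listed in Appendix 1". This is the Treated population.
- SAP 3.1: "Note that a patient may have received more than one of the Wright devices", and "patient level data will be included in the analysis for each device he/she received". The criterion is the device received, not the device still in place.
- The template for SAP Table 1.1 lists loss to follow-up, withdrawn consent, adverse event and other as reasons for discontinuation. Device removal has no line of its own.

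**The concern.** Protocol 7.1 and 7.3 count removal for implant failure as an event against the device in the survivorship analysis. Yet for a subject with a single study device, the same removal ends collection of the primary outcome. If it happens before the Final Clinical Follow-Up visit, that subject has no post-operative score at all, so even the first post-operative mean is affected.

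The rule also treats like subjects differently. Two people lose device A for the same reason. The one who also has device B stays in follow-up and counts towards A's mean; the one with only A does not. A's mean then depends on how often A is implanted alongside other study devices.

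What is at stake is the interpretation of the main performance result. A mean conditional on staying in the study would be presented to regulators and notified bodies as the result for everyone implanted. Neither Table 1.1 nor Table 3.1 would show how many scores are absent because of removal.

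**Working it through.** **1. The plan's own figure.** Protocol 6.2.6 and 7.2 give alpha 0.05 two-sided, half-width 0.1 and SD 0.313. Then n = (1.96 × 0.313 / 0.1)² = 37.63, rounded up to 38. The stated n = 38 reproduces. It concerns precision only and says nothing about who remains under observation.

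**2. Who contributes to device A's mean after A is removed.**

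| Subject | Follow-up (Protocol 6.2.2) | Counted for A (SAP 3.1) | In Treated population (SAP 5) |
|---|---|---|---|
| A still in place | continues | yes | yes |
| A removed, another study device remains | continues | yes, read literally | yes |
| A removed, no other study device | ends | no later score | yes |

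The third row is the gap between the stated population and the reported mean.

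**3. Formula.** Let p be the share whose device was removed before the visit, f the share of those who stay because another study device remains, and g the mean change in subjects with the device in place minus the mean change in removed subjects. Ignore other missing data.

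- Treated mean = (mean with device in place) − p·g
- Reported mean = (mean with device in place) − g·pf/(1 − p + pf)
- Bias = g·[p − pf/(1 − p + pf)], which is p·g when f = 0

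**4. Range.** The documents give none of p, f or g, so all three are assumptions. The upper g of 0.313 is one SD as quoted in the protocol; that is the SD of a post-operative score, not of a change, and serves only as a yardstick.

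| p | f = 0: g = 0.1 to 0.313 | f = 0.5: g = 0.1 to 0.313 |
|---|---|---|
| 2% | 0.002 to 0.006 | 0.001 to 0.003 |
| 5% | 0.005 to 0.016 | 0.002 to 0.008 |
| 10% | 0.010 to 0.031 | 0.005 to 0.015 |
| 20% | 0.020 to 0.063 | 0.009 to 0.028 |

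With f = 1 or g = 0 the bias is 0. With g = −0.1, p = 10% and f = 0 it is −0.010.

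**5. Example at the SAP's reporting threshold of 10 implanted patients.** Assume a change of 0.20 with the device in place, 0 after removal, and two removals.

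- Treated mean: (8 × 0.20 + 2 × 0)/10 = 0.16
- Both removed subjects leave: reported mean (8 × 0.20)/8 = 0.20, bias 0.04
- One of the two has another study device: reported mean (8 × 0.20 + 0)/9 = 0.178, bias 0.018

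The outcomes are the same, but the reported mean differs according to whether a removed subject has a second device.

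**6. Scale.** With SD 0.313 the half-width is 1.96 × 0.313/√40 = 0.097 at n = 40 and 1.96 × 0.313/√10 = 0.194 at n = 10 (0.224 with the t quantile). Every bias in the table is below these values. The interval does not allow for selective dropout, however, so its width does not correct the shift.

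No FAAM figure is computed, because the documents give no FAAM SD.

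**The case against.** A reader might infer four stronger things. The documents do not support them.

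- **That the means cover retained devices only.** The exception in Protocol 6.2.2 keeps multi-device subjects in, and SAP 3.1 counts data for each device received. Even that crediting is a literal reading, since the SAP does not address scores after removal.
- **That the bias is certainly upward.** Protocol 6.2.2 covers removal for any reason. The device list includes an external fixator (SALVATION External Fixation), for which removal need not mean failure. There are no removal rates, reasons or post-removal scores, so upward is the plausible direction and no more.
- **That removed subjects disappear from the results.** Removal for implant failure is a survivorship event (Protocol 7.3), device failure is tabulated by device (SAP 6.6), and a life table for it is listed (SAP Appendix 2, Table 5.2). The patient survey asks about removal (Protocol 6.3.5.3). What is missing is the link to the EQ-5D and FAAM results.
- **That all later adverse events are lost.** Protocol 11.4.1 asks for an adverse event form if a subject returns after the last scheduled follow-up and before the study is complete. That is partial capture.

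The other side can also say that exposure is modest: 38 of the 43 devices in SAP Appendix 1 have 1-year follow-up only, the analyses are descriptive without hypothesis tests, and at 2% to 5% removal the shift is at most 0.016. This stands, and it limits the size of the point. It does not close the gap between the stated population and the one averaged. It is also fair that scoring every removal as zero improvement would penalise removals unrelated to failure, and would override real scores of multi-device subjects if used as the main analysis.

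**Conclusion.** The concern holds in this limited form. Followed as written, the plan omits post-removal scores of single-device subjects, keeps those of multi-device subjects, and reports a mean that does not describe the Treated population. Improvement is probably overstated where removal follows failure or a complication.

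On the EQ-5D index the bias is about +0.002 to +0.063, given assumed removal of 2% to 20%, an assumed score gap of 0.1 to 0.313, and every removed subject leaving. It roughly halves if half of them stay with another study device. Sign and size both rest on assumptions that only the study data can replace. The point affects how the means are labelled and read; it does not invalidate the study.

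**What to change.** In the SAP:

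1. Add device removal to the discontinuation reasons in Table 1.1, split into failure or complication versus other. Show the number removed before each visit beside the means in Tables 3.1 and 3.2.1.
2. Add one sensitivity row per device in which subjects whose device was removed for failure or complication before the visit count as zero improvement for that device. Apply it identically to single- and multi-device subjects. Keep the observed-score analysis as the main result.
3. State that the main means are conditional on remaining in follow-up, and reconcile this with the Treated population in section 5.

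Optionally, continue the mailed EQ-5D, FAAM and patient survey after removal unless consent is withdrawn. This is a data-collection change only. It would need an approved amendment (Protocol 8.3) and could help only subjects still in follow-up or a successor study: enrolment stopped on November 1, 2021, and the SAP, effective 12 January 2022, already refers to a study end date. It cannot recover scores already missed.

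The SAP changes cost some table wording, one extra row per device and possibly a less favourable figure. They need no new patient contact, though the split by reason depends on what the adverse event and survey forms recorded. If removals are few, the row will show that the result is robust.
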